2.2.2 Randomization and Blinding

A total of up to 410 subjects will be recruited into this study and will be randomized in a 1:1 ratio to 15 mg losmapimod (BID) or placebo using an interactive/web voice response system (IxRS) for randomization. The randomization will be stratified by age (<65 or \geq 65) and requirement for oxygen at randomization (yes/no) at enrollment.

Only subjects who have completed screening assessments and are eligible for participation in the study will be randomized to receive study drug. Randomized subjects will be sequentially assigned a unique subject number from the randomization list per the IxRS. From the time of randomization and throughout the duration of the study, subjects will be identified by their unique randomization number.

The authorized site personnel will prepare the appropriate study drug for each subject based on the randomization schedule. Treatment codes should not be broken except in emergency situations, i.e., when knowledge of the treatment is essential for the immediate further management of the subject.

This study will be performed in a double-blind fashion. The investigator, study staff, subjects, sponsor, and monitor will remain blinded to subject-level treatment assignment until study closure. The investigational drug and its matching placebo are indistinguishable and will be packaged in the same way.

All doses will be administered either in the hospital (anticipated during the first week of study treatment) or taken by the study participants on an outpatient basis. The subject will bring the study treatment bottle to each visit (clinic or home assessment) for review by the site staff. The study treatment bottles will be collected at the Day 14 visit whether in the hospital or outpatient or at the ET visit if prior to Day 14.

2.2.3 Study Drug

Losmapimod will be provided in tablets of 7.5 mg for oral administration.

Matching placebo tablets will be provided for oral administration.

The tablets are plain white, round, biconvex, film-coated tablets. The proposed dosing regimen is as a twice daily dose of 15 mg (2 \times 7.5 mg tablets/dose BID). The proposed duration of treatment is for up to 14 days.

Subjects should take their dose of losmapimod or placebo with food whenever possible and with 240 mL of room temperature water.

2.2.4 Sample Size Determination

The primary efficacy endpoint of this study is the proportion of subjects who progress to death or respiratory failure by the end of study (Day 28). It is estimated that approximately 30% of enrolled subjects receiving SOC plus placebo will attain this endpoint. It is assumed that losmapimod will improve the primary endpoint by 40% over placebo. On the basis of these assumptions, a total of up to 410 subjects randomized to the losmapimod arm or the placebo arm in a 1:1 ratio (205 subjects in the losmapimod arm and 205 subjects in the placebo arm) will yield approximately 80% power in a 1-sided test at the 2.5% significance level.

The sample size estimate assumes an IA will be conducted after approximately 206 subjects (103 in the losmapimod arm, and 103 in the placebo arm) have completed the Day 28 visit, to assess early futility, using the rules specified in Section 5.1.

3 STATISTICAL METHODOLOGY

3.1 General Considerations

3.1.1 *Analysis Day*

Analysis day will be calculated from the date of first dose of study drug. The day of the first dose of study drug will be Day 1, and the day immediately before Day 1 will be Day -1. There will be no Day 0.

3.1.2 *Definition of Baseline*

Baseline is defined as the last measurement prior to the first dose of study drug.

3.1.3 *Summary Statistics*

Categorical data will generally be summarized with counts and percentages of subjects. The denominator used for the percentage calculation will be clearly stated. Continuous data will generally be summarized with descriptive statistics including n (number of non-missing values), mean (with its standard error), first quartile, median, third quartile, standard deviation, minimum, and maximum.

Where appropriate, descriptive statistics may be presented with 95% CI.

3.1.4 *Hypothesis Testing*

All statistical comparisons will be made using one-sided tests at $\alpha = 0.025$. All null hypotheses will be of no treatment difference, and all alternative hypotheses will be one-sided. Confidence intervals will be 2-sided with $\alpha = 0.05$ and reported to the same precision as the applicable summary statistic (e.g., mean), and standard error will be reported to one additional decimal place. P-values will be reported to four decimal places, with p-values less than 0.0001 reported as "<0.0001".

3.1.5 *Type I Error for Testing Key Study Endpoints*

The overall Type I error of the study will be controlled at 0.025 for 1-sided tests of hypotheses for the following key study endpoints, using a closed test procedure. The key endpoints will be tested in the fixed sequence procedure as the same sequence they are listed below. Assuming the analysis of the prior endpoint yields statistically significant treatment effect, the next key endpoint will be tested.

1. Proportion of progressors to death or respiratory failure by Day 28
2. Change in clinical status using the 9-point WHO scale at Day 14
3. Change in clinical status using the 9-point WHO scale at Day 7
4. Oxygen-free days by Day 28

3.1.6 Evaluation of Site Effect

Low enrolling sites will be pooled for analysis. For sites with less than 10 subjects in total, they will be pooled. Pooled sites will be only used for descriptive summary of biomarker endpoints of CRP and IL-6.

3.1.7 Adjustment of Covariates

In the event that the analysis models do not converge (e.g., due to sparse data), sex will be removed from the model, followed by the stratification factors until the model converges.

For mixed-model-repeated measures (MMRM) model, covariance structure will be updated to first-order autoregressive (AR(1)) prior to the removal of any covariate.

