8.6 Primary endpoints

- 1) Assuming p_t is probability of outcome in the losmapimod arm; p_c is the probability of outcome in the control arm

Study hypothesis: $H_0: p_t - p_c = 0$

$H_1: p_t - p_c < 0$

Assuming $p_t=0.18$, $p_c=0.30$, we can restate the hypothesis as

$H_0: \theta = \theta_0 = 0$

$H_1: \theta = \theta_1 = -0.12$

For the final analysis, the proportion of subjects achieving the primary endpoint in the treatment arms will be compared using an adjusted risk difference obtained from a regression model, adjusted for stratification factors, sex, and baseline CRP. Full details of the regression model will be provided in the SAP. An interim analysis to assess futility analysis—and potential sample size re-estimation—is discussed in [Section 8.9](#). All results will be summarized descriptively by treatment arm and

Fulcrum Therapeutics
Protocol FIS-001-2020

Losmapimod

expressed as proportions, along with corresponding unadjusted/adjusted 95% CI of the difference between response rates, and p-values.

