3.4 Efficacy Assessment

3.4.1 Primary Efficacy Endpoint

3.4.1.1 Primary Analysis

The primary efficacy endpoint is the proportion of subjects who progress to death or respiratory failure by Day 28.

Respiratory failure is defined as either need for mechanical ventilation (invasive or non-invasive) or high flow oxygen (defined by greater than 15 LPM flow of oxygen to maintain oxygen saturation between 90% and 95%), sustained for at least 48 hours, at any time during the study.

The fitted logistic regression model is used to predict the response rate for every subject in the study as if they had received the treatment or the control intervention.

Assuming p_t is probability of outcome in the losmapimod arm; p_c is the probability of outcome in the control arm

Study hypothesis: $H_0: p_t - p_c = 0$

$H_1: p_t - p_c < 0$

Assuming $p_t=0.18$, $p_c=0.30$, we can restate the hypothesis as

$H_0: \theta = \theta_0 = 0$

$H_1: \theta = \theta_1 = -0.12$

where θ is calculated as $p_t - p_c$. For the final analysis, the proportion of subjects achieving the primary endpoint in the treatment arms will be compared using an adjusted risk difference obtained from the logistic regression model, adjusted for stratification factors, sex, and baseline CRP. Sample SAS codes are provided in Appendix A. More details can be found in Guo et al. (2012) and Ge et al. (2011).

An interim analysis to assess futility analysis—and potential sample size re-estimation—will be conducted, as discussed in Section 5.1.

All results will be summarized descriptively by treatment arm and expressed as proportions, along with corresponding unadjusted/adjusted 95% CI of the difference between response rates, and p-values.

In the first step of multiple imputation, data will be multiple imputed using the FCS discriminant function separately by treatment arm to 20 imputed datasets. This analysis assumes data are missing at random. The imputation model will include the stratification factors, sex, baseline CRP, and a two-level binary factor (discharge from the hospital prior to discontinuing the study; Yes, No). [REDACTED]

For each imputed dataset, the proportion of subjects achieving the primary endpoint in the treatment arms will be compared using an adjusted risk difference obtained from the logistic regression model, adjusted for stratification factors, sex, and baseline CRP for each imputed dataset.

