6 CHANGES FROM PROTOCOL-SPECIFIED STATISTICAL ANALYSES

[figure not shown]
The statistical analysis plan introduced the following modifications to the analyses planned in the protocol:

[figure not shown]
1. Per Protocol, the FAS will consist of all subjects who are randomly assigned to receive double-blind study drug. Due to limited data, the FAS is updated to consist of all subjects who are randomized and receive any study drug.
2. Due to limited data, considerations on adjusting the model covariates have been added in the SAP.

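### The non-convergence fallback in SAP 3.1.7 can discard the randomisation strata while keeping baseline CRP; this costs precision, though almost never for the primary endpoint at planned size

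*SAP*

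**What the plan says.** Protocol 8.6 specifies that the primary endpoint is "compared using an adjusted risk difference obtained from a regression model, adjusted for stratification factors, sex, and baseline CRP", with the details left to the SAP. SAP 3.4.1.1 makes this a logistic model with the same covariates: "adjusted risk difference obtained from the logistic regression model, adjusted for stratification factors, sex, and baseline CRP". It is fitted to 20 imputed datasets and pooled by Rubin's rules.

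SAP 2.2.2 gives the randomisation strata as age below or above 65 and "requirement for oxygen at randomization (yes/no) at enrollment". Sex and CRP are not strata.

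SAP 3.1.7 adds a fallback for all analysis models. The trigger is non-convergence, with sparse data as the only example. The action is that "sex will be removed from the model, followed by the stratification factors until the model converges". For MMRM the "covariance structure will be updated to first-order autoregressive (AR(1)) prior to the removal of any covariate". SAP section 6 lists the rule as a departure from the protocol: "Due to limited data, considerations on adjusting the model covariates have been added in the SAP".

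The rule does not say:
- which of the two stratification factors goes first;
- what happens if the model with CRP alone also fails;
- whether the rule runs once or separately in each imputed dataset;
- whether the imputation model, which also contains the strata, changes with it.

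**The concern.** Stratified randomisation balances the arms within age and oxygen groups, so between-stratum variation no longer contributes to chance differences between arms. An analysis that leaves the strata out still counts that variation in its standard error. The standard error is then too large, and the gain from stratifying is lost. If covariates have to go, the randomisation factors should be the last to leave. The SAP instead puts them second and protects CRP, which was not used to randomise.

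Removing sex first will often not help. A logistic model on sparse data usually fails because one level of a binary covariate has no events. If that level belongs to a stratification factor, dropping sex changes nothing and the rule moves on to the strata. Methods exist that keep the strata and do not fail in this way.

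**Working it through.** **Inputs from the documents.** Event rates 30% and 18%; 205 per arm, 103 per arm at the interim; one-sided 0.025 (SAP 2.2.4 and 3.4.1.1). Boundaries z = -0.67873 and -1.91358 (SAP Table 2).

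**Inputs assumed, because the plan gives none.** 35% aged 65 or over; 70% on oxygen (90% in the sparse-outcome and 50-subject runs); the same odds ratio (OR) for each stratum factor, from 1 to 8; sex OR 1.3; CRP log-odds 0.4 per SD; blocks of 4.

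**Step 1: the plan's own power.** Variance term: 0.18 × 0.82 + 0.30 × 0.70 = 0.3576. Drifts: 0.12/√(0.3576/103) = 2.037 and 0.12/√(0.3576/205) = 2.873. Correlation: √(103/205) = 0.709. The bivariate normal probability of passing both boundaries is 0.0250 under the null and 0.802 under the alternative. The stated 2.5% and 80% reproduce, without any covariates.

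**Step 2: how often the rule would fire.** If a stratum level has m subjects with risk p, the chance of no events is (1 - p)^m.
- Planned rates, average risk (0.30 + 0.18)/2 = 0.24: 0.76^10 = 6%, 0.76^20 = 0.4%, 0.76^41 = 0.001%.
- Rare outcome, 5% against 3%, average 0.04, with 10% of 410 subjects (41) not on oxygen: 0.96^41 = 19%.

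Simulated non-convergence of the full logistic model:

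| Setting | Stratum OR | Non-convergence |
|---|---|---|
| Primary rates, N = 410, 70% on oxygen | 2, 4, 8 | 0.0% |
| Primary rates, N = 206, 70% on oxygen | 4 | 0.1% |
| Primary rates, N = 50, 90% on oxygen | 1 / 4 | 32% / 64% |
| 5% vs 3%, N = 410, 90% on oxygen | 1 / 4 | 20% / 62% |
| 5% vs 3%, N = 206, 90% on oxygen | 1 / 4 | 48% / 82% |
| 8% vs 5%, N = 410, 70% on oxygen | 2 | 0.6% |

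**Step 3: what dropping the strata costs.** The SAP's estimator (logistic model, predicted risks averaged over all subjects, delta-method standard error) was simulated at N = 410 with a single look at one-sided 0.025. The full model is compared with treatment plus CRP only, the end point of the rule.

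| Stratum OR | Power, full | Power, CRP only | Loss (points) | Type I, full | Type I, CRP only |
|---|---|---|---|---|---|
| 2 | 84.4% | 83.4% | 1.0 | 2.5% | 2.5% |
| 4 | 88.2% | 85.6% | 2.6 | 2.7% | 1.8% |
| 8 | 91.0% | 85.5% | 5.6 (0.9103 - 0.8547) | 2.8% | 1.5% |

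Monte Carlo error is about 0.5 to 0.7 points for power and 0.2 for type I error. A separate simulation of a Mantel-Haenszel risk difference stratified by age and oxygen gave type I error of 2.4 to 2.6%, so that fallback keeps close to the nominal 2.5%.

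**The case against.** The rule is pre-specified, disclosed in SAP section 6, and stepwise: the strata go only if dropping sex is not enough, and one of them may survive. The protocol left model details to the SAP. All of that stands. So does the point that the rule is close to irrelevant for the primary analysis at planned size. Day 28 mortality, where it could fire, lies outside the alpha-controlled sequence in SAP 3.1.5.

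The power loss in step 3 is measured at the primary event rates, where the rule does not fire. It shows what ignoring the strata costs, not an expected loss for the trial. In the rare-outcome runs a clean comparison is not available, because the full model can be scored only in the runs where it converged.

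A reader might infer more than the documents support:
- *That models fail because a stratum is strongly prognostic.* The SAP names only sparse data, and 20% to 48% of the rare-outcome runs failed with strata of no prognostic value. A prognostic stratum raises the chance but is not needed.
- *That the primary analysis stands to lose up to about 10 points of power.* That would compare adjustment with no covariates at all, whereas CRP stays in the model.
- *That the sponsor expects to use the rule on the primary endpoint.* Section 6 cites limited data but does not say for which analysis.
- *That different models will be pooled across imputations.* This is possible, but the SAP does not say so, and the sample code in Appendix A is not in the text available here.

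**Conclusion.** The removal order is the wrong way round for a stratified trial and should be changed, but this is a matter of efficiency and not of validity. When the strata are dropped, the test is conservative (type I error 1.5% to 2.5% in place of 2.5%) and gives up about 1 to 6 points of power for stratum odds ratios of 2 to 8.

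The chance that the rule fires is negligible for the primary endpoint at 206 or 410 subjects. It is substantial for rare outcomes with a small no-oxygen group, and for a trial or subgroup of around 50 subjects. These frequencies depend heavily on assumed values: with 70% on oxygen and an 8% against 5% outcome, failure falls to 0.6%.

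**What to change.** Rewrite SAP 3.1.7 as follows.

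1. For the logistic risk-difference analyses, if the model does not converge, refit the full covariate set by Firth's penalised likelihood, with the intercept corrected so that predicted risks average to the observed rate.
2. If that is not used or fails, report a Mantel-Haenszel risk difference stratified by age group and oxygen requirement. It needs no iteration.
3. In any other model where covariates must be removed, remove the non-stratification covariates first and the stratification factors last, and state the order between age and oxygen. For the logistic models this ordering is no substitute for steps 1 and 2, because dropping CRP cannot cure a stratum level with no events.
4. Use the same model for all 20 imputed datasets.
5. Leave the AR(1) step for MMRM as it is.

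The cost is a paragraph of text and some programming for the penalised fit and the stratified fallback. Penalised estimates shrink slightly, and the Mantel-Haenszel fallback gives up adjustment for sex and CRP.

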3.1.8 Handling of Dropouts and Missing Data

All missing or incomplete safety and PD data, including dates and times, will be treated as such. Missing test results or assessments will not be imputed, and as such, are assumed missing completely-at-random (MCAR).

For laboratory data, values below the limit of quantitation (recorded as “< LLQ”) will be set to half that limit.

For the analysis of hospital-free and ICU-free days, subjects who die prior to the analysis time point will have post-death days considered to be not hospital-free and not ICU-free.

Adverse events with missing start dates will be considered as treatment-emergent unless the partial date excludes that possibility, e.g., the adverse event month is prior to the first dose of study drug. Otherwise, the first day of the month will be used to impute missing start days and January will be used to impute missing start months. For example, if the first dose of study drug was on January 8, 2021 and an adverse event started in January 2021 with missing day, the start date will be imputed as the first dose date (January 8, 2021) and this adverse event will be considered as treatment-emergent. In the same example, if another adverse event has start month of December 2020 with missing day (before the first dose date of January 8, 2021), its start date will be imputed as December 1, 2020 and will not be considered as treatment-emergent.

Subjects who terminate the study prior to the analysis time point, not due to death, will be considered as missing for the analysis of key efficacy endpoints. Missing data in each treatment arm will be imputed using the observed data in their respective arm under the missing at random (MAR) assumption. Multiple imputation (MI) will be performed using the fully conditional specification (FCS) model. The imputation model will include the stratification factors, sex, and baseline CRP.

The handling of missing data for the key efficacy endpoints are outlined as the following:

1. Primary endpoint: patients whose status could not be ascertained (lost-to-follow up, etc.) will be imputed using multiple imputation approach.
2. Change in Clinical Status at Days 7 and 14: missing clinical status at the post-baseline timepoint will be imputed using multiple imputation approach.
3. Oxygen-free, ICU, hospitalized, respiratory failure-free days: subjects who die prior to the analysis time point will have post-death days considered not event free. For example, if a subject died on Day 6, Day 6 and after will not be counted toward oxygen-

free, ICU, hospitalized, respiratory failure-free days. Subjects who terminate the study for other reasons prior to the analysis time point will be imputed using multiple imputation approach.

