| Final Analysis | 205 | 205 | -1.91358 (0.02784) | -0.08009 | 0.97500 | -- | -- | 0.20000 |

Overall alpha=0.025 (1-sided); overall power=80%.

Abbreviations: MLE: maximum likelihood estimate.

Figure 1 Acceptance Region (Standardized-Z Scale)

[figure not shown]

Figure 2 Acceptance Region (P-value)

[figure not shown]
[figure not shown]

Figure 3 Acceptance Region (Maximum Likelihood Estimate)

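### SAP 3.1.8 gives two conflicting missing-data rules for the primary endpoint, and one of them, taken literally, sets an already observed respiratory failure to missing

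*SAP*

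**What the plan says.** SAP 3.1.8 first gives a rule for all key efficacy endpoints: "Subjects who terminate the study prior to the analysis time point, not due to death, will be considered as missing". Death is the only exception. Missing outcomes are then multiply imputed within arm under missing at random. The primary endpoint is first in the key-endpoint list in SAP 3.1.5, so the rule reaches it.

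The same section then lists the handling endpoint by endpoint. For the primary endpoint, item 1 says: "patients whose status could not be ascertained (lost-to-follow up, etc.) will be imputed using multiple imputation approach".

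SAP 3.4.1.1 defines the outcome: "The primary efficacy endpoint is the proportion of subjects who progress to death or respiratory failure by Day 28". Respiratory failure must last at least 48 hours and may occur at any point in the study. That section imputes 20 datasets separately by arm. Its visible model holds the stratification factors, sex, baseline CRP and an indicator of discharge before leaving the study; 3.1.8 lists the model without the discharge indicator. Redacted text follows the model in 3.4.1.1, and the sample code is not available. Protocol 8.3 leaves the imputation rules for the primary endpoint to the SAP.

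**The concern.** The endpoint is progression by Day 28, so it is settled once a qualifying failure has occurred. A subject who fails on Day 5 and withdraws consent on Day 10 is a progressor. The general sentence codes that subject as missing and draws an outcome from a model whose visible terms do not include earlier respiratory failure. Many of the draws would be non-events. Item 1 points the other way, since a documented failure is an ascertained status.

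Two programmers following the SAP could therefore code the same subject differently in the primary analysis. If the literal rule were used, event rates would fall in both arms and the difference would shrink. If leaving after respiratory failure were more common in one arm, the risk difference would be biased, in a direction set by which arm it was.

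**Working it through.** **Inputs from the documents.** SAP 2.2.4 gives the placebo rate ("It is estimated that approximately 30% of enrolled subjects receiving SOC plus placebo will attain this endpoint"), the effect ("It is assumed that losmapimod will improve the primary endpoint by 40% over placebo", so 0.30 × 0.60 = 0.18 and a difference of -0.12), and the allocation ("205 subjects in the losmapimod arm and 205 subjects in the placebo arm"). The design claim is that this "will yield approximately 80% power in a 1-sided test at the 2.5% significance level". SAP 5.1.1 gives the boundaries: stop for futility if z ≥ -0.67873 at 103 per arm; final critical value -1.91358 (one-sided p of 0.02784).

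**Reproducing the plan's figure.** Fixed-design power is Φ[(|d| - 1.960·se0)/se1], where se0 uses the pooled rate 0.24 and se1 the two separate rates. At 205 per arm, se0 = √(2 × 0.24 × 0.76/205) = 0.0422 and se1 = √((0.18 × 0.82 + 0.30 × 0.70)/205) = 0.0418. Power = Φ[(0.120 - 1.960 × 0.0422)/0.0418] = 81.4%. With the futility look (bivariate normal, correlation √(103/205), both boundaries to be passed), power is 80.2% with unpooled variance or 79.4% with pooled variance, and one-sided type I error is 0.0250. The stated 80% is confirmed.

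**Assumption.** Let q be the share of an arm's progressors who leave the study alive before Day 28 after a documented respiratory failure. The documents give no value. Suppose nobody else is missing.

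**Item 1 reading.** The failures are kept: 30% versus 18%, difference -0.120, fixed-design power 81.4%.

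**Literal general sentence.** The failures become missing and are imputed at the rate seen among the rest of the same arm. The expected arm rate becomes p(1-q)/[p(1-q) + (1-p)].

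- For q = 10%, placebo: 0.30 × 0.90 = 0.270, and 0.270/(0.270 + 0.70) = 0.278.
- For q = 10%, losmapimod: 0.18 × 0.90 = 0.162, and 0.162/(0.162 + 0.82) = 0.165.

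| q, placebo | q, losmapimod | Observed events set to missing (placebo / losmapimod) | Rates after imputation | Difference | Fixed-design power |
|---|---|---|---|---|---|
| 0 | 0 | 0 / 0 | 30.0% vs 18.0% | -0.120 | 81.4% |
| 5% | 5% | 3.1 / 1.8 | 28.9% vs 17.3% | -0.117 | 80.3% |
| 10% | 10% | 6.2 / 3.7 | 27.8% vs 16.5% | -0.113 | 79.1% |
| 20% | 20% | 12.3 / 7.4 | 25.5% vs 14.9% | -0.106 | 76.3% |
| 10% | 0 | 6.2 / 0 | 27.8% vs 18.0% | -0.098 | 66.0% |
| 15% | 5% | 9.2 / 1.8 | 26.7% vs 17.3% | about -0.095 | about 64% |

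The counts are 205 × p × q, for example 205 × 0.30 × 0.10 = 6.15. The last row barely depends on the draw probability. Using 0.3 in both arms gives 0.18 × (1 - 0.05 × 0.7) - 0.30 × (1 - 0.15 × 0.7) = 0.1737 - 0.2685 = -0.0948; the within-arm formula gives -0.0945.

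**No true effect.** Take 30% in both arms and q = 10% in the losmapimod arm only. The difference becomes 0.278 - 0.300 = -0.0216, with standard error √((0.278 × 0.722 + 0.300 × 0.700)/205) = 0.0448. The rejection rate in a fixed one-sided 2.5% test is Φ(-1.960 + 0.0216/0.0448) = Φ(-1.476), about 7%.

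These powers ignore the extra variance from multiple imputation, so they are slightly optimistic.

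**The case against.** The best defence is that the specific rule governs the general one. The numbered list is offered as the handling for each endpoint, and under item 1 a subject with a documented failure has an ascertained status and is not imputed. That is the sensible reading and probably the intended one. A reader might infer from the general sentence that the SAP deletes observed events from the primary analysis. The documents do not support that: item 1 stands beside it, and the redacted text and missing sample code could settle the coding.

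The defence does not remove the conflict. Nothing visible says that item 1 overrides the general sentence, or that an event observed before exit is kept. Item 1's own example, loss to follow-up, can be read as covering a subject who was lost after a documented failure. SAP 3.4.2 also builds several denominators from completers plus deaths, and says that death is not missing data without saying the same of respiratory failure.

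Three further points stand as limits on size:

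- The affected group is narrow. Protocol 3.4.2 asks for full follow-up after treatment stops and sets a demanding test for loss to follow-up. Non-death exits remain possible through withdrawn consent, loss to follow-up, or withdrawal for significant deviations (Protocol 10.3.2), and they are not replaced (Protocol 3.4.3).
- No exit rate, and no difference in exit between arms, can be taken from the documents.
- SAP 3.4.2 plans time-to-event sensitivity analyses of death, respiratory failure and their composite. A failure before exit would ordinarily count there, so a discrepancy might show. That does not alter the primary result.

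**Conclusion.** The concern holds as a conflict between two stated rules for the primary endpoint, one of which gives a wrong result if followed. It goes beyond missing detail, because the general sentence is explicit and exempts only death.

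The likely effect is small when exit is equal between arms: about 1 power point at 5% and about 2 at 10%. It becomes material only if exit after respiratory failure differs by arm. The 15% versus 5% case takes the difference to about -0.095; exit in the losmapimod arm alone can produce a spurious benefit. All of these sizes rest on assumed exit shares, on imputation at the within-arm rate, and on nobody else being missing. They illustrate what the literal rule could do and do not forecast what happened in the trial. Confidence that the visible text conflicts is high; confidence about which rule would be programmed is not.

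**What to change.** In SAP 3.1.8, exempt the primary endpoint from the general sentence, and put the same rule in 3.4.1.1. Suggested text: *For the primary endpoint, a subject with death or qualifying respiratory failure documented on or before Day 28 is counted as an event regardless of later discontinuation. Only subjects who are event-free at their last assessment and whose Day 28 status is unknown are multiply imputed.*

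In the same edit, align the two descriptions of the imputation model, since the discharge indicator appears in 3.4.1.1 but not in 3.1.8.

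The cost is a sentence or two in the SAP and a check that the code agrees. It needs no new data and no change to the design, sample size or boundaries. It should be settled before unblinded data are seen, so that the coding cannot be chosen with the results in view.
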